Other Adverse Reactions c , including Hemorrhage	

 
Intolerable Grade 2
 
Any Grade 3
 
	
 
Withhold TAFINLAR.
 
If improved to Grade 0-1, resume TAFINLAR at lower dose.
 
If not improved, permanently discontinue TAFINLAR.
 

First occurrence of any Grade 4	
 
Withhold TAFINLAR until improves to Grade 0-1, then resume at a lower dose.
 
Or
 
Permanently discontinue TAFINLAR.
 

 
Recurrent Grade 4
 
	Permanently discontinue TAFINLAR.

 
aNational Cancer Institute Common Terminology Crit
 
4.0.
 
bSee Table 6 for recommended dose reductions of TA
 
	·

<sup>cDose modification of TAFINLAR is not required for new primary cutaneous malignancies.

Confidential 37
December 31, 2019 Protocol Amendment 4

#### 5.5.1.3. Schedule Adjustments for Toxicity

• Dosing delays are permitted for either E6201 or dabrafenib. Once a toxicity has resolved to ≤ Grade 1, the subject may resume treatment. The dose level must be reduced to the next lower dose level when treatment is re- initiated following a delay for drug-related toxicity unless otherwise specified.

• The maximum delay allowed between treatment cycles for either E6201 or dabrafenib is 2 weeks. If toxicity has not resolved after 2 weeks of delay, the Medical Monitor should be contacted to discuss permission for resuming treatment after a longer delay for subjects who are experiencing clinical benefit.

#### **5.5.2.** Supportive Care Guidelines

- Medications may be administered for the management of symptoms associated with the administration of E6201 or dabrafenib, as required.
- Prophylactic pre-medication will not be used routinely. Adequate treatment for nausea and/or vomiting and diarrhea is permitted during Cycle 1. After Cycle 1, prophylaxis of nausea and/or vomiting and diarrhea is permitted.
- Granulocyte stimulating growth factors (e.g., G-CSF or GM-CSF) are allowed according to standard ASCO guidelines.
- Erythropoiesis-stimulating agents, transfusions, etc. are permitted for management of hematologic toxicities.

## 5.6. Criteria for Study Termination

If the sponsor, investigators, study monitor or regulatory officials discover conditions arising during the study that indicate that the study should be halted or that the study site should be terminated, this action may be taken after appropriate consultation between the sponsor and investigators.

Conditions that may warrant termination include, but are not limited to, the following:

- The discovery of an unexpected, serious, or unacceptable risk to subjects enrolled in the study
- A decision on the part of the sponsor to suspend or discontinue testing, evaluation, or development of the product
- Failure of an investigator to enroll subjects into the study at an acceptable rate
- Failure of an investigator to comply with pertinent FDA regulations
- Submission of knowingly false information from the study site to the sponsor, study monitor or the FDA
- Insufficient adherence to protocol requirements
- Study termination and follow-up would be performed in compliance with the conditions set forth in 21 CFR 312.50 and 21 CFR 312.56.

Confidential 38
December 31, 2019 Protocol Amendment 4

#### 6. STUDY POPULATION

#### 6.1. Subject Inclusion Criteria

Subjects must meet all of the following criteria to participate in the study:

- Males and females  $\geq$  18 years of age
- Histologically or cytologically confirmed Stage IV metastatic *BRAF* V600-mutated melanoma
- Documented metastasis of the primary tumor to the CNS
- *BRAF*-mutation melanoma tumor status will be established prior to entry based on previous *BRAF*-gene analysis reports from a CLIA qualified laboratory. If a report is not available, the mutation analysis will be performed at Screening on archival tissue.
- Other metastatic melanoma systemic disease allowed
- At least one measurable brain metastasis 0.5 3.0 cm, as assessed by MRI  $\leq$  3 weeks prior to initiation of study treatment, and does not require immediate local intervention (surgery or radiosurgery)
- Prior stereotactic radiosurgery and/or excision of up to 3 brain metastases is allowed > 3
  weeks before initiation of study treatment, provided neurological sequelae have resolved
  completely and at least one measurable metastasis with documented disease progression is
  present on MRI
- One prior line of immunotherapy for metastatic disease is allowed, if  $\geq 2$  weeks has elapsed between the end of therapy and initiation of study treatment
- Prior melanoma adjuvant immunotherapy is allowed, if  $\geq 6$  months has elapsed between the end of therapy and initiation of study treatment
- Prior melanoma adjuvant BRAF/MEK inhibitor treatment is allowed if  $\geq 12$  months has elapsed between the end of therapy and initiation of study treatment
- Able to swallow and retain oral medication with no clinically significant gastrointestinal abnormalities that may alter absorption, such as malabsorption syndrome or major resection of the stomach or bowels (Combination Safety Run-in and Expansion Phases of the study only)
- Asymptomatic or symptomatic CNS metastasis is allowed
- Stable dose of corticosteroids for CNS metastasis for  $\geq 7$  days is allowed
- Patients with seizures due to CNS metastases must be controlled with stable anti-epileptic treatment for ≥ 14 days
- Bisphosphonates and/or denosumab are allowed
- Adequate performance status: Eastern Cooperative Oncology Group (ECOG) ≤ 2 (APPENDIX A)
- Life expectancy of  $\geq 3$  months
- Adequate hematologic parameters without ongoing transfusional support:
  - Hemoglobin (Hb)  $\geq$  9 g/dL

Confidential 39
December 31, 2019 Protocol Amendment 4

- Absolute neutrophil count (ANC)  $\ge 1.0 \times 10^9 \text{ cells/L}$
- Platelets  $\ge 75 \times 10^9 \text{ cells/L}$
- Adequate renal and hepatic function:
  - O Creatinine  $\leq 1.5$  x the upper limit of normal (ULN), or calculated creatinine clearance  $\geq 50$  mL/minute x 1.73 m^2 per the Cockcroft-Gault formula (APPENDIX B)
  - $\circ$  Total bilirubin  $\leq 2$  times the upper limit of normal (ULN) unless due to Gilbert's disease
  - o ALT/AST  $\leq$  2.5 times ULN, or  $\leq$  5 times ULN for subjects with liver metastases
- Negative serum pregnancy test within 14 days prior to the first dose of study therapy for women of child-bearing potential (WCBP), defined as a sexually mature woman who has not undergone a hysterectomy or who has not been naturally post-menopausal for at least 24 consecutive months (i.e., who has had menses any time in the preceding 24 consecutive months). Sexually active WCBP and male subjects must agree to use adequate methods to avoid pregnancy (oral, injectable, or implantable hormonal contraceptive; tubal ligation; intra-uterine device; barrier contraceptive with spermicide; or vasectomized partner) throughout the study and for 28 days after the completion of study treatment.
- Ability to provide written informed consent

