### **Inclusion Criteria:**

- Males and females  $\geq 18$  years of age
- Histologically or cytologically confirmed Stage IV metastatic BRAF V600-mutated melanoma
- Documented metastasis of the primary tumor to the CNS
- *BRAF*-mutation melanoma tumor status will be established prior to entry based on previous *BRAF*-gene analysis reports from a CLIA qualified laboratory. If a report is not available, the mutation analysis will be performed at Screening on archival tissue.
- Other metastatic melanoma systemic disease allowed
- At least one measurable brain metastasis, 0.5 3.0 cm, as assessed by MRI  $\leq$  3 weeks prior to initiation of study treatment, and does not require immediate local intervention (surgery or radiosurgery)
- Prior stereotactic radiosurgery and/or excision of up to 3 brain metastases is allowed > 3 weeks before initiation of study treatment, provided neurological sequelae have resolved completely and at least one measurable metastasis with documented disease progression is present on MRI
- One prior line of immunotherapy for metastatic disease is allowed, if  $\geq 2$  weeks has elapsed between the end of therapy and initiation of study treatment
- Prior melanoma adjuvant immunotherapy is allowed, if  $\geq 6$  months has elapsed between the end of therapy and initiation of study treatment
- Prior melanoma adjuvant BRAF/MEK inhibitor therapy is allowed, if  $\geq$  12 months has elapsed between the end of therapy and initiation of study treatment
- Able to swallow and retain oral medication with no clinically significant gastrointestinal abnormalities that may alter absorption, such as malabsorption syndrome or major resection of the stomach or bowels (Combination Safety Run-in and Expansion Phases of the study only)
- Asymptomatic or symptomatic CNS metastasis is allowed
- Stable dose of corticosteroids for CNS metastasis for  $\geq 7$  days is allowed
- Patients with seizures due to CNS metastases must be controlled with stable anti-epileptic treatment for ≥ 14 days
- Bisphosphonates and/or denosumab are allowed
- Adequate performance status: Eastern Cooperative Oncology Group (ECOG) ≤ 2
- Life expectancy of  $\geq 3$  months

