#### 1.1.1. Measurable

*Tumor lesions:* Must be accurately measured in at least one dimension (longest diameter in the plane of measurement is to be recorded) with a minimum size of:

- 10mm by CT scan (CT scan slice thickness no greater than 5 mm)
- 10mm caliper measurement by clinical exam (lesions which cannot be accurately measured with calipers should be recorded as non-measurable)
- 20mm by chest X-ray

Malignant lymph nodes: To be considered pathologically enlarged and measurable, a lymph node must be  $\geq 15$ mm in short axis when assessed by CT scan (CT scan slice thickness recommended to be no greater than 5 mm). At baseline and in follow-up, only the short axis will be measured and followed. See also notes below on 'Baseline documentation of target and non-target lesions' for information on lymph node measurement.

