#### 1.1.2. Non-measurable

All other lesions, including small lesions (longest diameter <10mm or pathological lymph nodes with  $\geq 10$  to < 15mm short axis) as well as truly non-measurable lesions. Lesions considered truly non-measurable include: leptomeningeal disease, ascites, pleural or pericardial effusion, inflammatory breast disease, lymphangitic involvement of skin or lung, abdominal masses/abdominal organomegaly identified by physical exam that is not measurable by reproducible imaging techniques.

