## 2. Tumor response evaluation

## 2.1. Assessment of overall tumor burden and measurable disease

To assess objective response or future progression, it is necessary to estimate the overall tumor burden at baseline and use this as a comparator for subsequent measurements. Only patients with measurable disease at baseline should be included in protocols where objective tumor response is the primary endpoint. Measurable disease is defined by the presence of at least one measurable lesion (as detailed above in Section 1). In studies where the primary endpoint is tumor progression (either time to progression or proportion with progression at a fixed date), the protocol must specify if entry is restricted to those with measurable disease or whether patients having non-measurable disease only are also eligible.

Confidential 75
December 31, 2019 Protocol Amendment 4

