## 2.3.1. Evaluation of target lesions

Complete Response (CR): Disappearance of all target lesions. Any pathological lymph nodes (whether target or non-target) must have reduction in short axis to <10 mm.

Partial Response (PR): At least a 30% decrease in the sum of diameters of target lesions, taking as reference the baseline sum diameters.

Progressive Disease (PD): At least a 20% increase in the sum of diameters of target lesions, taking as reference the smallest sum on study (this includes the baseline sum if that is the smallest on study). In addition to the relative increase of 20%, the sum must also demonstrate an absolute increase of at least 5 mm. (Note: the appearance of one or more new lesions is also considered progression).

Stable Disease (SD): Neither sufficient shrinkage to qualify for PR nor sufficient increase to qualify for PD, taking as reference the smallest sum diameters while on study.

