# 2.3.2. Special notes on the assessment of target lesions

Lymph nodes. Lymph nodes identified as target lesions should always have the actual short axis measurement recorded (measured in the same anatomical plane as the baseline examination), even if the nodes regress to below 10mm on study. This means that when lymph nodes are included as target lesions, the 'sum' of lesions may not be zero even if complete response criteria are met, since a normal lymph node is defined as having a short axis of <10mm. Case report forms or other data collection methods may therefore be designed to have target nodal lesions recorded in a separate section where, in order to qualify for CR, each node must achieve a short axis <10mm. For PR, SD and PD, the actual short axis measurement of the nodes is to be included in the sum of target lesions.

Target lesions that become 'too small to measure'. While on study, all lesions (nodal and nonnodal) recorded at baseline should have their actual measurements recorded at each subsequent evaluation, even when very small (e.g. 2mm). However, sometimes lesions or lymph nodes which are recorded as target lesions at baseline become so faint on CT scan that the radiologist may not feel comfortable assigning an exact measure and may report themas being 'too small to measure'. When this occurs it is important that a value be recorded on the case report form. If it is the opinion of the radiologist that the lesion has likely disappeared, the measurement should be recorded as 0mm. If the lesion is believed to be present and is faintly seen but too small to measure, a default value of 5mm should be assigned (Note: It is less likely that this rule will be used for lymph nodes since they usually have a definable size when normal and are frequently surrounded by fat such as in the retroperitoneum; however, if a lymph node is believed to be present and is faintly seen but too small to measure, a default value of 5 mm should be assigned in this circumstance as well). This default value is derived from the 5mm CT slice thickness (but should not be changed with varying CT slice thickness). The measurement of these lesions is potentially non-reproducible, therefore providing this default value will prevent false responses or progressions based upon measurement error. To reiterate,

Confidential 77
December 31, 2019 Protocol Amendment 4

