## 2.4.1. Time point response

It is assumed that at each protocol specified time point, a response assessment occurs. Table 1 provides a summary of the overall response status calculation at each time point for patients who have measurable disease at baseline.

When patients have non-measurable (therefore non-target) disease only, Table 2 is to be used.

Table 1: Criteria for Overall Response for Target (+/- Non-target) Disease

Target Lesions	Non-Target Lesions New Lesions		Overall Response
CR	CR No		CR
CR	Non-CR/Non PD No		PR
CR	Not evaluated No PR		PR
PR	Non-PD or not all evaluated No		PR
SD	Non-PD or not all evaluated No		SD
Not all evaluated	Non-PD No		NE
PD	Any Yes or No PD		PD
Any	PD	Yes or No	PD
Any	Any	Yes PD	
CR = complete response, PR= partial response, SD=stable disease, PD= progressive disease, NE=inevaluable			

Table 2: Criteria for Overall Response for Non-target Disease Only

Non-Target Lesions	New Lesions	Overall Response
CR	No	CR
Non-CR/non-PD	No	Non-CR/non-PD
Not all evaluated	No	NE

Unequivocal PD	Yes or No	PD	
Any	Yes	PD	
CR = complete response, PR= partial response, SD=stable disease, PD= progressive disease, NE=inevaluable			

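### Entry accepts 0.5 cm brain lesions as measurable, both response appendices use 10 mm as reproduced, and the 3-of-18 rule names neither criteria set

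*Combined protocol and SAP*

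**What the plan says.** **Entry.** Section 6.1 requires "At least one measurable brain metastasis 0.5 3.0 cm, as assessed by MRI". The synopsis inclusion criteria say the same: "At least one measurable brain metastasis, 0.5 3.0 cm, as assessed by MRI". The range is 0.5 to 3.0 cm, and the lesion is called measurable.

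**Endpoint.** Section 10.4.1.1 defines intracranial objective response as a best response of CR or PR by RECIST 1.1 (Appendix E) and RANO-BM (Appendix F). Section 11.3.2.1 summarizes rates under both, with 95% intervals. Neither section ranks the two.

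**RECIST as reproduced.**
- Appendix E, 1.1.1 sets the minimum at "10mm by CT scan (CT scan slice thickness no greater than 5 mm" and lists no separate MRI figure.
- Appendix E, 1.1.2 classes as non-measurable "All other lesions, including small lesions (longest diameter <10mm or pathological lymph nodes with" a stated short axis, with no limit to one imaging method.
- Appendix E, 2.1: "Only patients with measurable disease at baseline should be included in protocols where objective tumor response is the primary endpoint".
- PR needs "At least a 30% decrease in the sum of diameters of target lesions, taking as reference the baseline sum diameters" (2.3.1).
- Section 2.4.1: "When patients have non-measurable (therefore non-target) disease only, Table 2 is to be used". The outcomes in that table are CR, non-CR/non-PD, NE and PD.

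**RANO-BM as reproduced.** Appendix F also defines measurable disease at 10 mm. It notes that guidance exists for investigators who choose 5 mm. Its CR and PR also depend on corticosteroid use and clinical status. It reports a working-group recommendation of RANO-BM for CNS response and RECIST 1.1 for non-CNS response.

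**Decision rule.** The synopsis and sections 5.1 and 11.1 treat 3 or more responses in 18 subjects as evidence to move forward, with no criteria set named.

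**The concern.** Two stated rules disagree on what counts as a measurable brain lesion, and the disagreement bears on the primary endpoint. A subject can enter on a lesion that the scoring rules, taken as written, do not accept as a target. If that lesion shrinks by half without vanishing, it may not be counted as a response.

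The deciding count is also undefined. The same scans can give different counts under the two sets, for three reasons: lesion size, the corticosteroid and clinical-status conditions in RANO-BM, and confirmation. Appendix E (2.4 and 2.6.1) requires confirmation in a non-randomized trial with response as primary endpoint; Appendix F as reproduced states no such rule. With a threshold of 3 responses, one or two reclassified subjects can change the conclusion. In an open-label study the choice of set should be fixed before responses are read.

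**Working it through.** **1. The passages side by side**

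| Source | Minimum measurable brain lesion |
|---|---|
| Section 6.1 and synopsis | 5 mm on MRI |
| Appendix E, 1.1.1 and 1.1.2 | 10 mm; below 10 mm is non-measurable |
| Appendix F | 10 mm by default; 5 mm as an option not adopted anywhere |

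Take a subject whose brain lesions are all 5-9 mm. Section 6.1 admits the subject. By Appendix E, 1.1.2 no brain lesion is measurable, so none can be a target and the 30% decrease in 2.3.1 has nothing to apply to. By 2.4.1 the non-target table applies, which offers CR but no PR. This last step is an inference, because 2.4.1 speaks of patients and not of organs. Appendix F has no equivalent table, so its scoring of such a subject under the 10 mm default is simply not stated.

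**2. The plan's own figure**

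Inputs from section 11.1: n = 18, success at 3 or more, null rate 0.05, target rate 0.25, stated power 80% and alpha 0.05. With X binomial:

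- P(X ≥ 3 | 18, 0.25) = 1 − (0.0056 + 0.0338 + 0.0958) = 0.865
- P(X ≥ 3 | 18, 0.05) = 1 − (0.3972 + 0.3763 + 0.1683) = 0.058

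The exact values differ from the stated 80% and 0.05. That is a separate matter; 0.865 and 0.058 serve here as the baseline.

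**3. If RECIST at 10 mm supplies the count**

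Assume that k of the 18 have only sub-10 mm brain lesions, that the true response rate is 25% in everyone, and that a fraction c of the responses in those k are CRs. The count is then the sum of a binomial (18 − k, 0.25) and a binomial (k, 0.25c). With c = 0 this reduces to P(X ≥ 3 | 18 − k, 0.25). For k = 3: 1 − (0.0134 + 0.0668 + 0.1559) = 0.764.

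| k | c = 0 | c = 0.5 |
|---|---|---|
| 0 | 0.865 | 0.865 |
| 2 | 0.803 | 0.835 |
| 3 | 0.764 | 0.818 |
| 4 | 0.719 | 0.800 |
| 6 | 0.609 | 0.759 |

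With no CRs the probability falls below 80% from k = 3. With half CRs it stays at 80% through k = 4 and is 0.781 at k = 5.

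**4. If a response under either set counts**

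Section 10.4.1.1 does not exclude this. The effect on the null rate is unknown. If it rose from 5% to 6%, P(X ≥ 3 | 18, 0.06) = 0.090, against 0.058. So the ambiguity can work in either direction.

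**The case against.** The strongest reply is that section 6.1 is itself the modification. It is trial-specific and calls a 0.5 cm lesion measurable, whereas Appendix E is largely reproduced guideline text that also covers matters foreign to this trial, such as CA-125 and PSA. Its 10 mm figure in 1.1.1 is given for CT and calipers, while brain assessment here is primarily by MRI. This reading is plausible and may be what was meant. But the protocol does not say that 6.1 overrides either appendix, and Appendix E, 1.1.2 classes lesions under 10 mm as non-measurable without reference to a method. The deciding set would still be unnamed.

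A second reply is that both rates are reported with intervals in an open-label Phase 1 study, so any discordance would be visible. That limits the harm, but visibility after the fact does not settle which count was meant to decide.

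A third is that the share of sub-10 mm subjects, the CR share and the discordance rate are all unknown. That stands: the calculations show sensitivity, not expected loss, and one or two such subjects are absorbed.

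A reader might infer that only RECIST conflicts with section 6.1. The documents do not support this, since Appendix F has the same 10 mm default.

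**Conclusion.** The conflict is real and should be resolved. Entry is at 5 mm, both endpoint appendices use 10 mm as reproduced, and the rule of 3 in 18 does not say which set supplies the count or how discordant results are handled. That a subject with only 5-9 mm brain lesions can score CR but not PR rests on reading Appendix E for the brain alone.

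The size depends on assumptions not in the documents. At a true 25% rate, with RECIST at 10 mm deciding, 2 to 6 such subjects take the probability of success from 0.865 to between 0.803 and 0.609 with no CRs, or between 0.835 and 0.759 if half their responses are CRs. Counting either set could instead raise type I error from 0.058 to 0.090.

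Three stronger readings are not supported:
- That the trial is underpowered. No document gives the number of affected subjects.
- That naming either set is enough. RECIST at 10 mm as the deciding set would leave the size conflict as it is.
- That a 5 mm limit fails under RECIST because of the rule for a lesion "faintly seen but too small to measure, a default value of 5mm should be assigned". A sole target would need a baseline of at least 5/0.7 = 7.1 mm to reach PR at that default. But the default covers only lesions too faint to measure; Appendix E, 2.3.2 records actual measurements below 5 mm, and 0 mm for a lesion judged to have gone.

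**What to change.** In sections 10.4.1.1, 11.1 and 11.3.2.1, before responses are read:

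1. Name RANO-BM as the set that supplies the 3-of-18 count, in line with the recommendation reported in Appendix F, and report intracranial RECIST 1.1 response as supportive.
2. State that intracranial target lesions are at least 5 mm on MRI, matching section 6.1, for RANO-BM and for the supportive RECIST reading. Alternatively, keep 10 mm for RECIST and report separately the subjects with no RECIST-measurable brain lesion.
3. State whether the deciding count uses confirmed responses, and report confirmed and unconfirmed counts.

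The cost is protocol and SAP wording. The scientific downside is that measurements of 5-9 mm lesions are noisier, so small changes are more open to measurement error. Confirmation is not a new burden for the RECIST reading, because Appendix E already requires it in this type of trial.
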